3.7 Analyses

Unit of Analysis and Sample Size Calculation

Patients within pairs (peer-peer coach dyads) will be the primary unit of analysis for the study. Thus, we calculated the sample size to adjust for the likely correlation between members of the pairs (intraclass correlation, or rho) in the intervention group. Accordingly, we calculated the sample size to provide 80% power to detect a difference between experimental groups of 0.5% in A1c with an alpha of .05, two-tailed.[95] We conducted the power analysis using the methods of Cohen and, based on the within-pair ICC of our prior reciprocal peer support intervention, adjusted for a within-pair intraclass correlation of 0.03 as implemented in STATA 12 software.[96] We estimated the standard deviation of a decline in A1c in this population (1.45) using data from our prior randomized controlled trials.[9,40] To provide the needed power, 148 subjects will be needed in each group (after attrition) and 74 peer mentors (clusters) across both groups (37 in each group). To conservatively allow for up to 15% attrition, a rate higher than occurred in any of our prior VA diabetes RCTs, we will recruit 174 patients for each arm, for a total of 348 patients, and a total number of 87 peer mentors. The estimate of the standard error of the change in BP was estimated from a database of actual BPs obtained in routine clinical practice for 24,000 patients with diabetes and hypertension in one large service network in the VA over a 24-month period in FY 2004-2005. It depends on both the variation in BP change at the person level and variability within person between measurements. We estimated the standard error for the change in blood pressure as 17 mmHg. Our target sample size will provide 90% power to detect a difference between experimental groups of 5 mmHg and differences between each of our key patient-centered outcome measures.

Approach to All Analyses

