We will follow international guidelines for analysis and reporting of clinical trials.[97] In the first phase (data verification), we will examine the distribution of all study variables to assess extreme values, missing data, variances, possible coding errors, skewness, and type of distribution. We will examine baseline data for clinically important differences across the two study groups for potential prognostic indicators, such as patients' age, race, comorbidities, and baseline use of services. Although we do not anticipate any imbalances due to the randomization, any differences between experimental arms in baseline characteristics will be included as covariates in analyses comparing outcomes. In the second phase of our outcomes analyses, we will evaluate possible bivariate associations between patients' experimental condition and the outcomes, as well as between each covariate and the outcomes, prior to fitting multivariable models. This will be done to determine unadjusted measures of effect, assess possible confounders, and anticipate any collinearity in subsequent analyses. In the final phase we will fit multivariable models to identify main effects.

Analysis Plans by Aim

Aim 1: Test the effectiveness of a technology-enhanced peer coaching (TEC) program in improving glucose control relative to peer support alone. Our past experience in similar patient populations

suggests that the primary endpoint from the trial (change in A1c) will be close to normally distributed. To assess the primary endpoint for Specific Aim 1 (change in mean HbA1c from baseline to 6 months), we will use a general linear mixed regression model:

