We will follow the same approach to comparing the observed usual care group with the peer support alone group. However, there is a higher likelihood of imbalances as the usual care group is observational, although they are drawn from the same eligibility pool as the participants. Therefore, we will include several key covariates in the analysis, including baseline A1c, age, gender, and race. We will also examine the data for differences in other potential prognostic indicators, such as baseline medication or service use, and include these variables in the regression if necessary. We will also need to examine whether biases may be caused by missing A1c data. Although the very high level of A1c testing in VHA is likely to lead to few missing data points, we will conduct sensitivity analyses using two approaches. In the first, we will assume that those with missing A1c levels at the end of the study had no improvement in their A1cs. In the second, we will use multiple imputation methods to fill in missing A1c values.

Aim 2: Assess the impact of the intervention on blood pressure and medication adherence as well as on key patient-centered outcomes, including patients' satisfaction and involvement with care, perceived social support, and diabetes-specific quality of life. For assessment of changes in systolic blood pressure and for the self-reported outcomes, we will use mixed effects models (similar to those in Aims 1) for

continuous outcomes, and generalized estimating equations (GEE) for ordinal outcomes with clustering.[98]

Aim 3: Identify patient characteristics associated with engagement in the intervention and mediators and moderators of the intervention's impact on patient outcomes. For these analyses, we will use multivariate modeling and path analyses.[99] Many of these outcomes will be measured using Likert scales. Thus, we will begin these analyses by developing contingency tables for ordered categorical data. We will then use generalized estimating equations (GEE), which are appropriate for modeling ordinal outcomes with correlated data.[99]

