We will use both quantitative and qualitative methods. We will compare patient characteristics and attitudes of participants and those not willing to participate in the study. For example, using VA administrative data, we will compare the characteristics of study participants (mean age, race, most recent A1C, co-morbidities) with those of diabetes patients treated in each site's outpatient clinics. Eligible refusals will be asked whether they would consent to a brief survey in which we will record information helpful in assessing the intervention's reach, such as diabetes distress, perceived need for support, interpersonal attachment styles, reasons for not enrolling, and existing sources of social support.

We will model independent associations and pathways linking intervention exposure to outcomes using nested multivariate regression. Subsequent nested models will introduce potential mediators, and we will evaluate changes in the magnitude of the relationship between experimental condition and outcomes before and after the covariates are introduced. Analyses of potential moderators will use standard approaches to evaluate potential interactions between these covariates and patients' experimental condition.[100] Independent variables and moderators will be centered before testing interactions, so that multicollinearity between first order and higher-order terms will be minimized. Statistically significant interactions will be interpreted by plotting regression lines for high and low values of the moderator variable. Stata routines greatly facilitate the plotting of these relationships.[101]

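### For Aim 3 outcomes kept ordinal, judging mediation by the change in the arm coefficient understates it under a logit or probit link, and no interval for an indirect effect is planned

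*SAP*

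**What the plan says.** SAP 3.7, Analysis Plans by Aim, covers mediation under Aim 3.

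- **Overall method:** "For these analyses, we will use multivariate modeling and path analyses". Nothing more is said about the path analyses.
- **Outcome type:** "Many of these outcomes will be measured using Likert scales". Which outcomes these are is not listed.
- **Model for the ordinal outcomes:** "We will then use generalized estimating equations (GEE), which are appropriate for modeling ordinal outcomes with correlated data". The link function is not given.
- **Mediation:** "We will model independent associations and pathways linking intervention exposure to outcomes using nested multivariate regression". Potential mediators enter in later models, and "we will evaluate changes in the magnitude of the relationship between experimental condition and outcomes before and after the covariates are introduced".

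The Aim 3 text defines no indirect effect, no scale for the comparison, and no test or interval.

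The Aim 1 outcome is continuous; the SAP expects that "the primary endpoint from the trial (change in A1c) will be close to normally distributed" and uses a linear mixed model. Aim 2 uses similar mixed models for systolic pressure and continuous self-reports, and GEE for ordinal outcomes. Protocol 3.6.2 lists the candidate mediators in Table 2. It also describes the patient-centered outcomes, which range from twelve-item scales to a two-item distress measure.

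**The concern.** Comparing the arm coefficient before and after a mediator enters is the difference-of-coefficients method. In a linear model the difference equals the indirect effect. Under a logit or probit link it does not, because the coefficient is non-collapsible. Once a predictor of the outcome enters, less unexplained variation is left on the latent scale, and a non-null arm coefficient grows in absolute size even if the arm never affected that predictor. The two nested coefficients are then on different scales, and their difference mixes rescaling with mediation. GEE does not cure this, because it averages over clusters and not over covariates.

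At stake is the Aim 3 account of how the intervention works on the ordinal survey outcomes. A real mediator could look weaker than it is, and a variable that mediates nothing could show a negative share and be mistaken for a suppressor. Without an interval, the reader cannot tell either from noise.

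**Working it through.** **Sample size (the plan's only relevant figure).** The documents give no mediation figure, so the planned size is reproduced first. SAP 3.7 specifies "80% power to detect a difference between experimental groups of 0.5% in A1c with an alpha of .05, two-tailed", with SD 1.45 and ICC 0.03.

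- Per arm, unclustered: 2 × (1.960 + 0.842)² × 1.45² / 0.5² ≈ 132.02, rounded up to 133.
- Patients per mentor: 148 / 37 = 4. Design effect: 1 + (4 − 1) × 0.03 = 1.09.
- 133 × 1.09 = 144.97. In whole clusters of 4 this is 37 clusters, or 148 per arm, as stated.
- Trial-size runs therefore use 2 × 148 = 296 patients in 74 clusters.

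**Assumptions not in the documents.** Logit link; five categories; direct arm log odds ratio c = 0.5; mediator effect b = 0.5, 1.0 or 1.5 log-odds per SD; arm-to-mediator effect a = 0 or 0.3 SD. Apparent share mediated = 1 − adjusted / unadjusted arm coefficient. True share = ab / (ab + c).

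**Approximation.** The logistic error variance is about 3.29. Leaving out a mediator of unit SD divides the arm coefficient by about s = √(1 + b²/3.29), which is 1.037, 1.142 and 1.298 for the three values of b. With no mediation the apparent share is about 1 − s: −4%, −14% and −30%. With a true 50% it is about 1 − s/2: 48%, 43% and 35%.

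**Large-sample simulation** (proportional odds, 300,000 patients):

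| a | b | Unadjusted | Adjusted | Apparent share | True share |
|---|---|---|---|---|---|
| 0 | 0.5 | 0.479 | 0.502 | −5% | 0% |
| 0 | 1.0 | 0.426 | 0.504 | −18% | 0% |
| 0 | 1.5 | 0.377 | 0.507 | −34% | 0% |
| 0.3 | 0.5 | 0.624 | 0.504 | 19% | 0.15/0.65 = 23% |
| 0.3 | 1.0 | 0.688 | 0.513 | 25% | 0.30/0.80 = 37.5% |
| 0.3 | 1.5 | 0.695 | 0.494 | 29% | 0.45/0.95 = 47% |

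Repeat simulations, including runs of 40,000 and 100,000 patients per scenario with equal-frequency categories, agree. With no mediation they give about −5% to −6%, −16%, and −31% to −36%. With a true 50% they give about 47%, 38–43% and 28–34%, and 17–22% at b = 2.0.

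**Limits of the effect.**

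- Null arm effect (a = 0, c = 0): the coefficient changes by at most 0.005.
- Full mediation (c = 0, a = 0.3): the apparent share is 99–101%.
- Linear model, b = 1: the difference is −0.002 at a = 0, and 0.299 against a true 0.30 at a = 0.3.

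**At trial size** (ordinal GEE, 74 clusters of 4, ICC about 0.03, 300 replicates):

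| a | b | Mean change | Target ab | Bias | Chance SD | Size of bias / SD |
|---|---|---|---|---|---|---|
| 0 | 0.5 | −0.014 | 0 | −0.014 | 0.055 | 0.25 |
| 0 | 1.0 | −0.076 | 0 | −0.076 | 0.103 | 0.74 |
| 0 | 1.5 | −0.131 | 0 | −0.131 | 0.142 | 0.92 |
| 0.3 | 1.0 | 0.18 | 0.30 | −0.12 | 0.107 | 1.1 |

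**On a common scale.** Replace the mediator in the reduced model by its residual after regression on arm. The reduced arm coefficient becomes c + ab and the full one stays c. The difference is ab: 0 when a = 0, and 0.30 when a = 0.3 and b = 1.

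**The case against.** The other side has a good deal to say.

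- **The model is not pinned down.** No link is stated, and the nested regressions are not expressly called ordinal GEE. This stands: logit or probit is an assumption, although logit is the usual choice. The silence is itself something to fix.
- **Few outcomes may be touched.** A1c and systolic pressure have linear models, and so may the multi-item scales in Protocol 3.6.2. This stands and sets the scope, but the SAP itself says many Aim 3 outcomes are Likert-type and sends them to ordinal GEE.
- **Path analysis is named** and could estimate indirect effects directly. This stands in part. The SAP does not say what the path models estimate or how they relate to the nested models, whose comparison is the only mediation procedure described.
- **No threshold or share mediated is defined.** True; the share is used here only to express size. The bias lies in the difference of coefficients, however it is summarized.
- **The bias is lost in noise.** It is negligible at b = 0.5 and below one chance SD in all three no-mediation runs. In the one trial-size run with real mediation it is about one SD. Even so, its direction is known and it can be removed at little cost, and noise of this size is the reason an interval is needed.

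A reader might infer that Aim 3 as a whole will misstate mediated effects, or that its conclusions about mechanism will be wrong. The documents do not support that. The linear models are exempt, the error attenuates real mediators and does not invent false ones, and nothing moves when the arm effect is null.

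**Conclusion.** The point holds for Aim 3 outcomes that are kept ordinal, provided the link is logit or probit. There, the change in the arm coefficient understates mediation: slightly for a mediator worth 0.5 log-odds per SD, and by roughly 7 to 22 percentage points of a true 50% for one worth 1.0 to 1.5. These sizes rest on assumed effects, since the documents give none. In a single trial of 296 patients the bias is of the same order as chance variation.

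Two gaps do not depend on the link: no interval for an indirect effect is stated for any outcome, and the role of the path analyses is undefined. The primary A1c comparison and the sample size are untouched. The change is worth making because the planned comparison is biased in a known direction for these outcomes and a better method is available.

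**What to change.** Revise the Aim 3 text in SAP 3.7 to:

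1. list which outcomes stay ordinal and which are analyzed as continuous scores, and state the link for the ordinal GEE;
2. for continuous outcomes, report the indirect effect as a product of coefficients, for example from the path analysis already named, and say how that analysis relates to the nested models;
3. for ordinal outcomes, compare the nested models on a common scale, for example with the mediator residualised on arm in the reduced model, or by contrasts of predicted probabilities;
4. give each indirect effect a 95% interval from a bootstrap that resamples mentors together with their patients.

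The cost is SAP wording and slightly more analysis work. No new data are needed.

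### Aim 3 reads mediation from the raw change in the arm effect between nested models; where these are ordinal logit or probit models, that change understates same-direction mediation and can cancel it

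*SAP*

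**What the plan says.** The Aim 3 text in SAP section 3.7 (Analysis Plans by Aim) sets out the method in three steps.

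- It names the tools in general terms: "For these analyses, we will use multivariate modeling and path analyses".
- It describes the outcomes and their model: "Many of these outcomes will be measured using Likert scales", followed by ordered contingency tables, and then "We will then use generalized estimating equations (GEE), which are appropriate for modeling ordinal outcomes with correlated data".
- It describes the mediation analysis: "We will model independent associations and pathways linking intervention exposure to outcomes using nested multivariate regression". Mediators are added in later nested models, and "we will evaluate changes in the magnitude of the relationship between experimental condition and outcomes before and after the covariates are introduced".

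The text gives no link function, no common scale for the two coefficients, no estimator of an indirect effect, and no test or confidence interval for the change. Table 2 in Protocol section 3.6.2 lists six candidate mediators. Under Aims 1 and 2 the SAP assigns linear mixed models to A1c change, systolic blood pressure and continuous self-reported outcomes.

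**The concern.** Comparing the arm effect before and after a mediator enters is sound in a linear model: if the arm does not move the mediator, the expected arm coefficient stays the same. An ordinal logit or probit model fixes its residual variance by convention. When a variable that predicts the outcome enters, unexplained variation falls, and every coefficient is re-expressed in units of the smaller residual. A non-zero arm coefficient therefore grows, whether or not the arm affects that variable.

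The before/after change is then a mixture of mediation and rescaling. When the indirect and direct effects have the same sign, mediation shrinks the arm coefficient and rescaling enlarges it, so the two offset. When they have opposite signs, the raw change exaggerates suppression. A larger sample, or a confidence interval around the raw difference, would not remove the bias.

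At stake is half of a secondary aim: which of the six candidate mediators carries the effect on the Likert outcomes. Readings from the ordinal models would also not be comparable with those from the linear A1c and blood pressure models.

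**Working it through.** **Inputs from the SAP (Unit of Analysis and Sample Size Calculation).** The trial has "80% power to detect a difference between experimental groups of 0.5% in A1c with an alpha of .05, two-tailed", SD of A1c change 1.45, ICC 0.03, 148 patients and 37 mentors per arm after attrition, and 174 recruited per arm. The documents give no figure for mediation, so these serve only to set a trial size and an effect size.

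**The plan's own figure.** n = 2 × (1.960 + 0.842)² × 1.45² / 0.5² = 132.0 per arm. With 148/37 = 4 patients plus the mentor per cluster, the design effect is 1 + (5 - 1) × 0.03 = 1.12, and 132.0 × 1.12 = 147.9, so 148. Then 148/0.85 = 174.1, against 174 stated. The figure reproduces. The standardised effect is 0.5/1.45 = 0.345. Applying it to a Likert outcome is an assumption.

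**Rescaling formula.** Take a latent outcome Y* = c′·arm + b·M + e and a mediator M = a·arm + u, with u of unit variance. The full model estimates c′/σₑ. The reduced model estimates (c′ + ab)/√(σₑ² + b²). Write p = ab/(c′ + ab) for the true mediated share and R² = b²/(σₑ² + b²) for the latent variance the mediators explain. Then

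apparent share = 1 - full/reduced = 1 - (1 - p)/√(1 - R²).

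This holds for probit with a normal mediator and is approximate for logit. At R² = 0.30, √0.70 = 0.837. So p = 0 gives 1 - 1/0.837 = -19.5%, and p = 0.5 gives 1 - 0.5/0.837 = 40.2%. At p = 1 the apparent share is 100% whatever R² is, so complete mediation is not masked.

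**Large-sample simulation.** Five-level outcome, arm effect about 0.34 SD, R² = 0.30. Ranges are across separate runs.

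| True share | Formula | Probit, raw change | Logit, raw change | Logit, mediator residualised on arm |
|---|---|---|---|---|
| 0% | -19.5% | -20% | -22% to -25% | -1% |
| 20% | 4.4% | 5% | -2% to 1% | 21% |
| 30% | 16.3% | 17% | 11% to 14% | 31% |
| 50% | 40.2% | 40% | 38% | 51% |

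**Sensitivity to mediator strength, with no mediation.**

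| Latent variance explained | Formula | Logit, raw change |
|---|---|---|
| 7% | -3.7% | about -4% |
| 20% | -11.8% | -14% to -16% |
| 30% | -19.5% | -22% to -25% |
| 40% | -29.1% | -32% to -37% |

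The 7% row is the logit case b = 0.5, c′ = 0.6, where 0.25/(3.29 + 0.25) = 7% and the arm effect is 0.6/√3.54 = 0.32 SD. The arm log odds goes from 0.590 to 0.616.

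**Where the two effects cancel (logit, c′ = 0.6).** No visible change occurs at a true share of about 4% for b = 0.5, 15% for b = 1.0 and 26% for b = 1.5.

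**Trial size.** With 2 × 148 = 296 patients, a = 0.2, b = 1.0 and c′ = 0.6 (300 replicates, clustering not simulated), the true indirect effect is 0.2 × 1.0 = 0.20. The mean raw change is 0.08, and it is zero or negative in 21% of trials. On a common scale the mean is 0.20, and 7% are zero or negative.

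**The case against.** The strongest reply is that the plan may never do this. The mediation paragraph speaks of nested multivariate regression without calling it ordinal, and of a relationship's magnitude rather than a logit coefficient. Most patient-centred measures in Protocol section 3.6.2 are multi-item scales (two of twelve items, one of five, one of two). Their scores could go into the linear mixed models that Aim 2 provides for continuous outcomes, where the problem does not arise. Aim 3 also names path analyses, which can give an indirect effect as a product of paths.

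Much of this stands. That the nested models are ordinal is an inference, though a natural one: GEE for ordinal outcomes is the only outcome-specific model Aim 3 names. The path analyses do not close the gap, because no estimator is specified and the before/after comparison is the only mediation procedure spelled out.

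A reader might go further and infer any of the following, none of which is supported:

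- That real mediation is hidden altogether. Exact cancellation needs a particular share for each mediator strength; a true 50% still shows as about 38%, and complete mediation stays visible.
- That the strongest mediators always suffer most. The bias grows with variance explained at a fixed mediated share. At fixed variance explained it shrinks as the share rises: at 30% explained the shortfall is 22 to 25 points at a true share of 0% and 50 - 38 = 12 points at 50%.
- That the plan tests the change at 5%, reports a mediated share, or treats no change as no mediation. It states none of these. The share is used here only to express size.

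**Conclusion.** The point holds conditionally. Where Aim 3's nested models for Likert outcomes use an ordinal logit or probit link, the raw before/after change in the arm coefficient is a biased guide to mediation, and the comparison as described would mislead. Under the assumptions above with 30% of latent variance explained, no mediation looks like suppression of about 22 to 25%, and a true 20% share looks like none. If the mediators explain only 7%, the distortion is about 4 points and of little consequence. The documents give no mediator strength, so where this trial falls in that range is unknown.

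The scope is secondary Aim 3 only. The A1c endpoint, the sample size, blood pressure and any scale score fitted by a linear mixed model are untouched. This is a worthwhile, inexpensive correction rather than a threat to the trial's main conclusion.

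**What to change.** In the Aim 3 mediation paragraph:

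1. State for each outcome whether it is fitted by a linear mixed model or by ordinal GEE and, for the latter, the link.
2. Limit the raw before/after comparison of the arm coefficient to outcomes fitted by linear mixed models. Multi-item scores that are near-continuous can go here.
3. For outcomes fitted by ordinal GEE, estimate the indirect effect on one scale. This can be the product of the arm-to-mediator and mediator-to-outcome paths. Alternatively, compare the full model with a reduced model containing the mediators residualised on arm and covariates (Karlson-Holm-Breen).
4. Give a confidence interval for the indirect effect from a bootstrap that resamples mentors with their patients.

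The cost is SAP wording and a few lines of code, with no new data or patients. The downside is slightly more analysis work and a sentence of explanation in the report.
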